9.5. Analysis methods – primary outcome(s)

A template for reporting the primary outcome will be given in a separate template report.

The primary outcome is the proportion of women randomised who experience a live birth at and beyond 34 weeks of gestation. The denominator of this proportion will be all women randomised and the numerator will be those women who have conceived during the six ovulation induction cycles (maximum 240 days) and have gone on to have a live birth at or beyond 34 weeks.

A mixed effects binomial regression model will be used to calculate the risk difference (identity link) and relative risk (log link) with 95% confidence intervals for the primary outcome (live birth \geq 34 weeks), adjusting for the randomisation variables listed in section 4.6. If this primary method doesn't converge, the plan detailed in section 9.1 will be followed.

Statistical significance of the treatment group parameter will be determined (p-value generated) through examination of the associated chi-squared statistic (this will be obtained from the log-binomial model which produces risk ratios).

Summary data of the primary outcome in the form of frequencies and percentages will be produced that looks at the primary outcome for all the combinations of treatments (combinations A-D as per section 6.2 Baseline characteristics).

In the event of babies from a multiple pregnancy having different pregnancy outcomes, if at least one of the babies had a live birth \geq 34 weeks then this will count as a live birth \geq 34 weeks overall. If all those babies within that multiple pregnancy have the same pregnancy outcome (e.g. all are live births) then this will only be counted as one outcome (event).

See section 9.1 for covariate adjustment and model convergence.

9.6. Analysis methods – secondary outcomes

A template for reporting the secondary outcomes will be given in a separate template report. See section 9.1 for covariate adjustment and model convergence.

Dichotomous outcomes (e.g. pregnancy loss and APGAR score <7) will be analysed using the same regression approach as the primary outcome, using the denominators detailed in section 5.3. Pregnancy events will be limited to those who conceived during the six ovulation induction cycles (maximum 240 days). For pregnancy end outcomes, in the event of babies from a multiple pregnancy having different outcomes, for example one live birth and one miscarriage, both the events will be counted in the separate categories (i.e. they will contribute to both a live birth event and a miscarriage event.

Mixed-effects Poisson regression will be used for count data (number of ovulation induction cycles to live birth) with an Incidence Rate Ratio (IRR) and confidence interval generated (if there is evidence of overdispersion then a negative-binomial model will be fitted instead). This outcome will be reported as count data (i.e. 1, 2, 3, 4, 5, and 6).

For continuous secondary outcome measures (e.g. birthweight and gestational age) means and standard deviations will be reported alongside adjusted mean differences (with confidence intervals) estimated using a mixed effects linear regression model.

A Cox Proportional Hazard (PH) model (provided the assumptions of proportionality are met) will be utilised for time to event data (time from randomisation to pregnancy). Data will be summarised with medians and interquartile ranges and estimates of difference presented as adjusted hazard ratios (with confidence intervals). A Kaplan Meier plot will be produced to assess the data visually. In this model, randomising centre will be regarded as a shared frailty.

Mode of birth will be analysed as unassisted vaginal versus any other category; all categories of data will be presented.

For birthweight, babies from multiple births will be included as separate babies. To allow for the clustering at the mother level a robust variance estimator clustered by mother will be included in the model. If this does not work (e.g. failure to converge) then analysis on the mother's level will be used instead and the outcome interpreted as such.

For the following neonatal outcomes the denominator will be number of mothers and not the number of babies. In the event of multiple babies from the same pregnancy having different outcomes, e.g. if one twin had an early infection, and the other did not, this event will still be classified as having occurred:

- Discharge to hospital
- Early infection
- Retinopathy of prematurity
- Necrotising enterocolitis
- Intraventricular haemorrhage
- Respiratory distress syndrome
- Ventilation or oxygen support

Ovulation rate will be converted to a percentage score (Total number of ovulations / Total number of ovulation induction cycles) and so will be treated as continuous proportion data. Data will be summarised separately by allocation group using mean and standard deviation. Since this is a proportion, the data will be bounded between the values [0, 1] and so a fractional regression model using a logit link will be fitted with cluster-robust standard errors. Marginal effects will be derived as mean differences in proportions between the groups and the associated 95% confidence intervals.

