5.3. Analysis populations

Participants will be analysed in the treatment group to which they were randomised, regardless of treatment compliance. Analysis populations will be as follows:

- Primary outcome, live birth at or beyond 34 weeks: all randomised participants. Analyses will also be produced using women who achieved pregnancy, defined as a positive pregnancy test (urine or serum beta-hCG test >10 mIU/ml), as the denominator but this will be treated as supportive evidence only)
- Secondary outcomes:
 - (Treatment outcomes) Ovulation rate, time from randomisation to pregnancy: all randomised participants
 - (Treatment outcomes) Number of ovulation induction cycles required for pregnancy: women who achieved pregnancy (defined as a positive pregnancy test (urine or serum beta-hCG test >10 mIU/ml))
 - (Pregnancy end outcomes) Ongoing pregnancy at 12 weeks (range 11⁺⁰ to 14⁺⁰ weeks) of gestation, pregnancy loss (defined as pregnancy loss <24 weeks of gestation), termination, stillbirth, molar pregnancy, pregnancy of unknown location, ectopic pregnancy, multiple live births: all randomised participants (analyses will also be produced using women who achieved pregnancy, defined as a positive urine or serum beta-hCG test >10 mIU/ml, as the denominator but this will be treated as supportive evidence only)
 - Time from conception to delivery (gestational age at live birth), gestational age <28/<32/<37 weeks, singleton live births at and beyond 34 completed weeks of gestation, live births at and beyond 37 completed weeks of gestation, mode of birth (unassisted vaginal, instrumental vaginal, elective caesarean section, emergency caesarean section, vaginal breech birth, other), number of ovulation induction cycles to live birth ≥24 weeks : women with live birth ≥24 weeks
 - Birth weight, APGAR score (at 1, 5 and 10 minutes) and APGAR score <7 out of 10 (at 1, 5 and 10 minutes): babies born alive ≥24 weeks
 - Antenatal outcomes: women achieving pregnancy
 - o Intrapartum outcomes: women with live birth≥24 weeks
 - Post-partum outcomes: women with live birth≥24 weeks
 - Maternal outcomes: all randomised participants

- Neonatal outcomes: babies born alive ≥24 weeks.
- Survival at 28 days of neonatal life: babies born alive ≥24 weeks
- Safety outcomes:
 - \circ Neonatal congenital or chromosomal abnormalities: babies born alive ≥24 weeks

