9.1. Covariate adjustment

Both group allocations (as a result of the double randomisation required by the factorial design) will be included in all analysis models (for comparisons A and B only as for C, D and E this would not be possible as we are only looking at one of the randomisations. See section 4.12 Trial comparisons for details on the comparisons); no interaction of treatment effect is assumed in the first instance but this will be explored through supportive analyses (section 9.10).

In the first instance, intervention effects between groups for all outcomes will be adjusted for the minimisation parameters listed in section 4.6 in the same form as entered into the minimisation algorithm, i.e. categorical variables such as age will remain as such in the model, rather than converting them to the continuous form (as this creates a problem downstream in terms of presentation of the subgroup analyses). Randomising centre will be included as a random intercept in the model, and all other factors as fixed effects (with the exception of time to event outcomes where centre will be regarded as a shared frailty).

A mixed effects binomial regression model will be used to calculate the risk difference (identity link) and relative risk (log link) with 95% confidence intervals for the primary outcome (live birth \geq 34 weeks), adjusting for the randomisation variables listed in section 4.6. If the binomial model fails to converge then, in the first instance, a Poisson regression model with randomising centre as a random effect and robust standard errors will be used to estimate the relative risk. In the case that the Poisson regression model still does not converge, randomising centre will be removed and the log-binomial model will be refit for just fixed effects. If this also fails, covariates will be dropped as described in section 9.1. A Poisson model will not estimate the risk difference, so if the initial model fails to converge, the same process of variable removal will be followed, within a log-binomial model framework. The p-value relating to the intervention group parameter as generated by the model estimating the relative risk will be presented.

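### Four outcomes counted per baby have no sibling rule in the SAP, so their intervals and one safety p-value will be somewhat too precise if siblings' outcomes are positively correlated

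*SAP*

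**What the plan says.** **Unit of analysis (SAP 5.3).** The baby is the unit for birthweight and APGAR score, and also for:
- APGAR below 7: "APGAR score <7 out of 10 (at 1, 5 and 10 minutes): babies born alive ≥24 weeks"
- 28-day survival: "Survival at 28 days of neonatal life: babies born alive ≥24 weeks"
- the safety outcome: "Neonatal congenital or chromosomal abnormalities: babies born alive" (from 24 weeks)
- the neonatal outcomes as a group: "Neonatal outcomes: babies born alive ≥24 weeks"

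**Sibling rules (SAP 9.6).** There are two.
- For birthweight, multiples enter as separate babies and "a robust variance estimator clustered by mother will be included in the model". If that does not work, the analysis moves to the level of the mother.
- Seven neonatal outcomes (discharge to hospital, early infection, retinopathy, necrotising enterocolitis, intraventricular haemorrhage, respiratory distress, ventilation or oxygen) use the number of mothers as denominator. One affected baby makes the event positive.

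**Models.** SAP 9.6 sends dichotomous secondary outcomes, naming APGAR below 7, to the primary-outcome regression with the denominators of 5.3. Continuous outcomes go to a mixed linear model. The clustering term is centre: "Randomising centre will be included as a random intercept in the model" (SAP 9.1).

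**Testing.** SAP 5.1 and 5.2 give safety outcomes p-values without multiplicity adjustment. SAP 9.8 names a test only for SAEs and SUSARs.

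**Twin sensitivity analysis.** Protocol 13.2.2 counts both twins in the first instance and promises to examine the effect of doing so. SAP 9.10 restricts sensitivity analyses to the primary outcome.

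**The concern.** The SAP recognises that siblings are not independent. It corrects for this in birthweight and avoids it in seven other outcomes, but leaves four per-baby outcomes without a rule. Those four go into models designed for one record per woman. A centre random intercept captures only what babies in the same centre share, not what two babies of the same mother share. If twins' outcomes are positively correlated, the effective number of observations is below the number of babies. Intervals are then too narrow and the congenital-abnormality p-value too small.

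Twins are a live issue in this trial. Protocol 1.2.2 links clomifene to roughly a tenfold higher risk of multiple pregnancy than natural conception and suggests fewer multiples with letrozole. The twin share may therefore differ between the arms being compared.

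**Working it through.** **1. Which outcomes are exposed**

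| Outcome | Unit in SAP 5.3 | Sibling rule in SAP 9.6 | P-value |
|---|---|---|---|
| Birthweight | baby | variance clustered by mother, or mother level | no |
| Seven neonatal outcomes | baby | mother denominator (contradicts 5.3) | no |
| APGAR score | baby | none | no |
| APGAR below 7 | baby | none | no |
| 28-day survival | baby | none | no |
| Congenital abnormality | baby | none | yes (safety) |

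Multiple pregnancy, OHSS and SAEs are counted per randomised woman, so congenital abnormality is the only per-baby safety outcome.

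**2. The plan's own figures.** Neither document gives a twin share, a within-pair correlation or a design effect. The nearest figures are the revised power statements, which reproduce (two-sided 5%, pooled variance, 1:1). With 380 per arm at 44% vs 34%, power is 80.8% (stated 81%). With 760 per arm at 39% vs 29%, it is 98.5% (stated 98.5%). The planning rates give the approximate number of mothers with a live birth from 34 weeks:
- letrozole vs clomifene, or metformin vs placebo: 760 × 0.39 + 760 × 0.29 = 296 + 220, about 517
- the two combination arms: 380 × 0.44 + 380 × 0.34 = 167 + 129, about 296

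**3. Equal risk in singletons and twins.** Let t be the share of pregnancies that are twin and r the within-pair correlation (both assumed). The fraction of babies who are twins is f = 2t/(1+t), and DE = 1 + f·r.
- t = 5%: f = 0.10/1.05 = 0.095
- r = 0.3: DE = 1.029, √DE = 1.014, true size of a nominal 5% test 5.3%
- r = 0.5: DE = 1.048, √DE = 1.024, size 5.6%
- r = 0.8: DE = 1.076, √DE = 1.037, size 5.9%

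Size is 2[1 − Φ(1.96/√DE)]. Over the wider grid t = 2 to 10% and r = 0.2 to 1, DE runs from 1.008 to 1.182 and size from 5.1 to 7.1%.

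A simulated per-baby two-proportion test, with the mother counts of step 2 and event rates of 3 to 10%, agrees. Size was 4.8 to 5.2% at r = 0, 5.2 to 5.6% at t = 3 to 5% with r = 0.5, and 5.5 to 6.2% at t = 3 to 5% with r = 1.

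**4. Events concentrated in twins.** With event rates p_s in singletons and p_t in twins, let S = (1−t)·p_s(1−p_s) and T = 2t·p_t(1−p_t). Then DE = 1 + r·T/(S+T). Assume 28-day death of 0.5% in singletons.

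| t | p_t | r | S | T | DE | √DE |
|---|---|---|---|---|---|---|
| 3% | 4% | 0.5 | 0.00483 | 0.00230 | 1.16 | 1.08 |
| 3% | 5% | 0.7 | 0.00483 | 0.00285 | 1.26 | 1.12 |
| 5% | 4% | 0.5 | 0.00473 | 0.00384 | 1.22 | 1.11 |
| 5% | 5% | 0.7 | 0.00473 | 0.00475 | 1.35 | 1.16 |

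The correct standard error is 8 to 16% larger than the naive one. Equivalently, the naive one is 7 to 14% too small (1 − 1/1.08 to 1 − 1/1.16).

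**5. Birthweight.** Under a centre random intercept, two mothers in the same centre share a random effect, so the independent units are centres. A variance clustered by mother sits below that level and is not coherent with the model. To see whether clustering by mother leaves the interval too narrow, a linear outcome was simulated with 516 mothers in 45 centres, twin share 3 to 10%, within-pair correlation 0.6, SD 500 and a 900-unit twin shift (all assumed; 3,000 runs per setting). Ignoring siblings gave size 7.8 to 8.5%. Clustering by mother gave 4.7 to 5.8%. The fitted model was ordinary regression without a centre random intercept, so this shows that clustering by mother deals with siblings. It does not validate the exact SAP specification.

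**The case against.** **Stronger readings that the documents do not support.**
- A reader might infer that every per-baby outcome except birthweight ignores siblings. SAP 9.6 moves seven of them to a mother denominator, which removes the dependence. Their defect is the contradiction with 5.3.
- A reader might infer that the birthweight interval is too narrow. Both the rule and its fallback handle siblings, and step 5 gives no sign of undercoverage. What remains is an incoherent specification and a fallback that does not say which value represents a mother of twins.
- A reader might infer that the safety p-values in general are affected. Only the one for congenital abnormality is. Its model has to be inferred, because 9.8 does not name one; Protocol 13.2.2 points to the primary-outcome approach.

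**Size.** The best counter-argument is that the effect is small. The general case changes standard errors by only a few percent. The larger figures concern 28-day survival, which gets no p-value, and rest on rates that are not in the documents. Under those rates there would also be very few deaths: 517 × (0.97 × 0.005 + 0.06 × 0.04) = 3.7 up to 517 × (0.95 × 0.005 + 0.10 × 0.05) = 5.0. Sparse data would then matter more than clustering. This count starts from births at 34 weeks or later, so it leaves out earlier births. The argument stands and limits the importance of the point, but it does not supply the missing rule.

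**The fallback model.** SAP 9.1 falls back on a Poisson model with robust standard errors if the binomial model fails. Clustered at mother or centre, those would cover siblings. The level is not stated, so this cannot be relied on.

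**Conclusion.** The point holds for APGAR score, APGAR below 7, 28-day survival and congenital or chromosomal abnormality. As written, siblings are treated as independent in these four, and the error is anti-conservative if siblings correlate positively. With 5% twins and correlation 0.3 to 0.8, correct standard errors are about 1.5 to 4% larger, and the congenital-abnormality test would have a true size of about 5.3 to 5.9%. If 28-day deaths concentrate in twins as assumed in step 4, the figure is 8 to 16%. Twin share, correlation and event rates are all assumptions.

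Two further defects stand without any assumption: the denominators of the seven neonatal outcomes conflict between SAP 5.3 and 9.6, and the protocol's twin sensitivity analysis has no counterpart in the SAP. The primary outcome is untouched, because SAP 9.5 counts a multiple birth once. The point does not threaten the trial's main conclusions, but it should be corrected.

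**What to change.** In SAP 9.6, give each of the four outcomes a sibling rule:
- **APGAR below 7, 28-day survival, congenital abnormality.** One option is to extend the existing mother-level rule, under which one affected baby makes the event. This keeps the planned binomial model and the risk difference. Survival should then be reversed, so that the event is any death by 28 days. The other option is a per-baby model whose variance allows for clustering within mother. That model must be compatible with the centre term. If it is a Poisson model, SAP 9.1 itself notes that the risk difference is lost.
- **APGAR score and birthweight.** Use random intercepts for mother nested in centre. Define the per-mother summary for the birthweight fallback (for example the mean of the siblings).

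Also:
- align SAP 5.3 with 9.6 on the seven neonatal outcomes;
- name the model and test for congenital abnormality in SAP 9.8;
- restore in SAP 9.10 the protocol's sensitivity analysis for counting both twins.

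The cost is a few sentences and a little more analysis, with no new data. Intervals become slightly wider. The mother-level option changes the question from risk per baby to risk per mother, which should be stated when results are reported.

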9.7. Analysis methods – other outcomes

Any data that does not form a pre-specified outcome will be presented using simple summary statistics by intervention group (i.e. numbers and percentages for binary data and means (or medians) and standard deviations (or inter-quartile ranges) for continuous normal (or non-normal) data.

9.8. Safety data

The number and percentage of participants experiencing any serious adverse events (SAEs) and suspected unexpected serious adverse reactions (SUSARs) will be presented by intervention group. Statistical significance will be determined (p-value generated) through examination of the associated chi-squared statistic. The total number of SAEs and SUSARs in each group will also be given along with a descriptive table of the details of the events. For side effect data, summary statistics (e.g. frequency and percentage) will be detailed only.

A template for reporting this safety data will be given in a separate template report.

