# 9. ADVERSE EVENT REPORTING

### **9.1** Definitions

Adverse Event	AE	Any untoward medical occurrence in a participant or clinical trial subject administered a medicinal product and which does not necessarily have a causal relationship with this treatment.
Adverse Reaction	AR	All untoward and unintended responses to an IMP related to any dose administered.
Serious Adverse Event	SAE	
 
Any untoward medical occurrence or effect that:
 
Results in death is life-threatening*
 
Requires hospitalisation or prolongation of existing hospitalisation
 
Results in persistent or significant disability or incapacity
 
Is a congenital anomaly/birth defect
 
Or is otherwise considered medically significant by the Investigator**
 

Serious Adverse Reaction	SAR	An Adverse Reaction which also meets the definition of a Serious Adverse Event
Unexpected Adverse Reaction	UAR	An AR, the nature or severity of which is not consistent with the applicable product information (e.g. Investigator Brochure for an unapproved IMP or (compendium of) Summary of Product Characteristics (SPC) for a licensed product).  When the outcome of an AR is not consistent with the applicable product information the AR should be considered unexpected.
Suspected Unexpected Serious Adverse Reaction	SUSAR	A SAR that is unexpected i.e. the nature, or severity of the event is not consistent with the applicable product information.  A SUSAR should meet the definition of an AR, UAR and SAR.

 LOCI PROTOCOL
 Sponsor's reference: RG\_18-272
 v1.0 07-Nov-2019
 Page 37 of 57

 IRAS ID: 257918
 EudraCT number: 2018-004641-16
 ISRCTN: TBC

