## 9.2 Reporting Requirements

The collection and reporting of Adverse Events (AEs) will be in accordance with the UK Policy Framework for Health and Social Care (2017) and the requirements of the Health Research Authority (HRA). Definitions of different types of AEs are listed in the table of abbreviations and definitions. The Investigator should document all AEs experienced by the trial participant in the source data and assess the seriousness and causality (relatedness) with reference to the Reference Safety Information (RSI). The RSI is based on section 4.8 'Undesirable Effects' of the Summary of Product Characteristics (SmPC) located in the 'SmPC Reference Document'.

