## 9.7 Assessment of Expectedness by the CI

The CI or delegate(s) will also assess all related SAEs for expectedness with reference to the following criteria.

Category	Definition
Expected	An adverse event that is consistent with known information about the trial related procedures or that is clearly defined in the relevant safety information.
Unexpected	An adverse event that is not consistent with known information about the trial related procedures.

Table 6. Definitions of serious adverse event expectedness

The CI will undertake review of all SAEs and may request further information from the clinical team at site should be made available immediately upon request. The CI will not overrule the severity or causality assessment given by the site Investigator but may add additional comment on these. If the event is unexpected (i.e. is not defined in the approved version of the RSI, it will be classified as a Suspected Unexpected Serious Adverse Reaction (SUSAR).

**LOCI PROTOCOL** Sponsor's reference: RG\_18-272 v1.0 07-Nov-2019 Page 41 of 57 IRAS ID: 257918 EudraCT number: 2018-004641-16 ISRCTN: TBC

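### SAP 9.8, read as written, puts a significance test on SUSARs, a category that leaves out every listed serious reaction and so does not compare drug safety

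*SAP*

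**What the plan says.** SAP 9.8 sets out the number and percentage of women with any event in two categories: "serious adverse events (SAEs) and suspected unexpected serious adverse reactions (SUSARs) will be presented by intervention group". The next sentence reads: "Statistical significance will be determined (p-value generated) through examination of the associated chi-squared statistic". It does not say which of the two it applies to. Where the two sentences meet, SUSARs stand immediately before the test: "suspected unexpected serious adverse reactions (SUSARs) will be presented by intervention group. Statistical significance will be determined (p-value generated"). The one exemption is at the end of the paragraph: "For side effect data, summary statistics (e.g. frequency and percentage) will be detailed only". Total numbers of SAEs and SUSARs and a descriptive table of events are also promised.

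The protocol defines a SUSAR by what the product information leaves out. Section 9.1: "A SAR that is unexpected i.e. the nature, or severity of the event is not consistent with the applicable product information". Section 9.2 gives the reference: "The RSI is based on section 4.8 'Undesirable Effects' of the Summary of Product Characteristics (SmPC"). Section 9.7 gives the rule: an unexpected event, meaning one that "is not defined in the approved version of the RSI, it will be classified as a Suspected Unexpected Serious Adverse Reaction (SUSAR").

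Three other parts of the SAP bear on this:

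- Sections 4.4 and 5.3 name serious adverse events as a safety outcome with an analysis population. SUSARs appear in neither list.
- Section 9.7 gives simple summary statistics to data that do not form a pre-specified outcome.
- Section 5.2 leaves safety tests unadjusted for multiplicity, and section 4.12 applies the methods to each comparison unless stated otherwise.

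**The concern.** A p-value for SUSARs invites the reader to treat it as evidence on which drug is safer. The category cannot carry that meaning. Whether a related serious event counts depends on whether it is listed, not on how often it occurs or how grave it is. An excess of listed serious reactions on one drug would not enter the test at all.

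The SAP is also inconsistent with itself. It tests in 9.8 something that it does not list as an outcome in 4.4 and that 9.7 would leave descriptive.

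There is a conditional problem as well. If expectedness is finally settled against the SmPC of the drug actually received, the same reaction could be a SUSAR in one arm and an expected reaction in the other, and equal harm could then appear as a difference. Finally, SUSAR counts are likely to be small, and the SAP names no exact test for sparse tables.

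**Working it through.** **1. Arm sizes.** SAP 4.7 (revised sample size) gives 1600 randomised for comparisons A and B, which is 800 per arm at 1:1, and 1520 with outcome data, which is 760 per arm. As a check, the stated power of 98.5% for 39% vs 29% reproduces. With pooled rate 0.34:

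- SE under the null = √(2 × 0.34 × 0.66 / 760) = 0.02430
- SE under the alternative = √((0.39 × 0.61 + 0.29 × 0.71) / 760) = 0.02417
- z = (0.10 − 1.96 × 0.02430) / 0.02417 = 2.17, so power = 98.5%

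Comparison C has 800 randomised, 400 per arm. SAP 5.3 uses all randomised women for SAEs, so 800 and 400 are the denominators below. The documents give no SUSAR rate, so every event count below is an assumption. The 5% level is stated for the primary outcome and assumed here for the safety p-values.

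**2. What the test leaves out, on any reading of expectedness.** Suppose 8 of 800 women in one arm and 0 of 800 in the other have a listed, related serious reaction. A comparison of related SAEs gives p = 0.005 (step 3). The SUSAR counts are 0 vs 0, and the SUSAR test sees nothing.

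**3. Sparse counts.** For k/n vs 0/n the Pearson statistic without correction reduces to 2nk / (2n − k), and the smaller expected count is k/2. At n = 800:

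| SUSARs | Chi-squared | Uncorrected p | Yates p | Fisher p | Smaller expected count |
|---|---|---|---|---|---|
| 3 vs 0 | 1600 × 3 / 1597 = 3.006 | 0.083 | 0.25 | 0.25 | 1.5 |
| 4 vs 0 | 1600 × 4 / 1596 = 4.010 | 0.045 | 0.13 | 0.12 | 2 |
| 6 vs 0 | 1600 × 6 / 1594 = 6.023 | 0.014 | 0.041 | 0.031 | 3 |
| 8 vs 0 | 1600 × 8 / 1592 = 8.040 | 0.005 | 0.013 | 0.008 | 4 |

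At n = 400, 4 vs 0 gives 800 × 4 / 796 = 4.020, p = 0.045. The uncorrected test thus turns significant at four events against none, where an exact test does not. With fewer than four SUSARs in total it cannot reach p < 0.05.

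**4. The conditional bias.** Assume that both arms have the same true rate of a related serious reaction, that it is listed for one drug only, and that expectedness follows the drug received. The SUSAR count is then 0 in one arm, and the test rejects whenever the other arm has four or more events. At 800 per arm the binomial probability of that is:

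- true rate 0.25% (mean 2 events): 14%
- true rate 0.5% (mean 4): 57%
- true rate 1% (mean 8): 96%

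If only half of the reactions are listed for the one drug, the rejection rates are 6%, 12% and 19%. At 400 per arm with full listing they are 2%, 14% and 57%.

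**5. After the change.** If the test counts related serious events regardless of expectedness, equal harm of 4 vs 4 gives p = 1.00. At 800 per arm, under equal harm, the uncorrected test then rejects in 4.1% to 5.1% of trials for true rates of 0.25% to 2%.

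**The case against.** The strongest objection is that the documents point away from the bias in step 4. Protocol 6.2.5 has cases judged serious, unexpected and related first, and unblinded afterwards at the Trial Office for reporting. Protocol 9.2 speaks of one SmPC reference document, and 9.7 of one approved RSI. An assessor who does not know the allocation cannot apply one drug's SmPC to one arm and another's to the other. No section describes reclassifying events after unblinding. This largely stands: a blinded judgement against a pooled reference would remove most of the label-driven imbalance. It does not settle the matter, because neither document says that the reference is pooled, and the 9.1 definition leaves room for the allocated drug's own SmPC.

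A second objection is that the p-value sentence may be meant for SAEs only, since SAP 5.1 and 5.2 promise p-values for safety outcomes and SUSARs are not one. That is possible. But the preceding sentence names both categories and only side effects are exempted, so the text would still need correcting.

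Three stronger readings are tempting and not supported:

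- *That the SUSAR test does compare labels between arms.* No section states per-drug judgement, and the documents do not show that any serious event is listed for one ovulation drug and not the other. The rates in step 4 are assumptions.
- *That placebo women have no product information to be judged against.* Placebo replaces metformin only; every woman also receives letrozole or clomifene.
- *That the plan would hide a true difference in serious harm.* SAEs are compared regardless of expectedness, and totals and event details are given by group.

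The protocol also calls the safety profile well established (9.3) and exempts many hospitalisations from SAE forms (9.4.1), so there may be too few SUSARs for the test to matter.

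**Conclusion.** The point holds in a limited form. As written, SAP 9.8 tests SUSARs. That conflicts with SAP 4.4 and 9.7. Whichever reference is used for expectedness, the test leaves out all listed serious reactions and so does not measure comparative drug safety.

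That equal harm could test as a difference is conditional. It requires expectedness to be settled against the allocated drug's SmPC, and a related serious reaction that is listed for one drug and not the other. Under those assumptions, four events against none at 800 per arm is enough for the uncorrected chi-squared (p = 0.045) but not for Fisher's test (p = 0.12). The sparse-count weakness exists without any labelling assumption.

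The effect is confined to a safety p-value. The primary outcome and its analysis are untouched. The change is worth making because it is cheap and prevents a p-value that could be misread as a drug-safety finding.

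**What to change.** In SAP 9.8:

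1. State that the p-value applies to women with any SAE.
2. Add a comparison of women with any causally related SAE, regardless of expectedness, using the blinded investigator's causality assessment. Protocol 9.6 also lets the Chief Investigator classify an event as related, so say which assessment defines the variable.
3. List SUSARs by arm descriptively, without a test.
4. Specify an exact test where expected counts are small.

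The cost is SAP wording only. Causality is already recorded on the SAE form (Protocol 9.6), so no new data are needed. The edit should be made before the trial statistician is unblinded for the final analysis (SAP 5.6).
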